## **5.2 Analysis of primary outcome**

We will use linear mixed model analysis to estimate mean difference in ISI between the two groups at 3, 6 and 12 months of follow-up, with the primary outcome measurement at 3 months. The model will include participant ID as a random effect and time, time–group interaction and baseline covariates as fixed effects. Of baseline covariates we will include age, sex, and education. Determination of possible categorizing of the covariates will be done before unblinding and published in an updated version of this SAP.

The assumption of normally distributed residuals will be assessed by visual inspection of histograms and Normal Q-Q plots. Model assumptions for mixed models will be checked: residuals (approximately) normally distributed and homogeneity of residual variance (homoscedasticity).

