## **2. Study design**

### **2.1 Study design**

The trial is as a cluster-randomized clinical trial with two parallel groups, investigating the effects of dCBT-I on insomnia symptoms for patients with comorbid musculoskeletal complaints and insomnia in inpatient rehabilitation compared with traditional inpatient rehabilitation only (figure 1). To maximize the number of participants receiving the additional treatment (dCBT-I), the participants are randomized to the intervention and usual care at a ratio of 2:1.

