### **2.2 Randomization and treatment assignment**

The randomization will be at group level to avoid contamination between members of the same rehabilitation group. Each group are randomized using a computer-generated block randomization provided by the Clinical Research Unit (Project support) at the Faculty of Medicine and Health Sciences at the Norwegian University of Science and Technology (third party).

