### 2.3 Determination of sample size

We anticipated that around five of 10 patients will have insomnia within each rehabilitation group and that the average Insomnia Severity Index (ISI)-score for participants completing usual treatment will be 15 ( $SD = 4$ ). An average 4-point improvement on the ISI score is considered a meaningful change. In order to maximize the number of participants receiving the additional treatment (dCBT-I), we will randomize the participants to the intervention and usual care at a ratio of 2:1. Recruiting 15 clusters with 2:1 randomization will achieve 80% power to detect a 4-point difference between the intervention and usual treatment group, with a conservative assumption that the intraclass correlation is 0.2 and the coefficient of variation in cluster size up to 0.7, and with a significance level of 5%. This would mean that around 150 participants will be screened to give an expected sample size of 75 (50 in dCBT-I + usual care and 25 in usual care). We expect a dropout rate of approximately 20% and that around 50% of the participants in the intervention group will complete at least four of the dCBT-I modules. Given that the per-protocol analysis is of particular interest in this study, we aim to recruit 21 clusters to account for the fact that we expect an average of four participants per cluster in the control group to complete the follow-up, and an average of two participants in the intervention group to complete at least four of the modules and attend the follow-up.

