### **3. Statistical principles**

#### **3.1 Confidence intervals and p-values**

We will use two-sided tests and report mean differences with 95% confidence intervals.

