### **5.2.1 Sensitivity analyses**

We do not anticipate strong cluster-level effects; however, we will conduct a sensitivity analysis including rehabilitation group in the mixed linear model with follow-up timepoints as level 1, participants as level 2, and rehabilitation group as level 3.

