## 5.3 Analysis of secondary outcomes

For binary secondary outcomes (e.g., clinically relevant change in ISI, minimal important change in PSFS), we will use a generalized estimated equation logistic model to estimate the odds ratio (OR) for achieving at least an 8-point improvement in ISI score. In these analyses, we will assume an exchangeable correlation structure and a robust variance estimator. For the other secondary outcomes, a mixed linear regression model will be used.

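### Rehabilitation groups are randomised, but the primary model omits them, so any positive within-group correlation makes its 95% CI too narrow and its type I error exceed 5%

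*SAP*

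**What the plan says.** The design is clear about the unit of randomisation. Section 2.1: "The trial is as a cluster-randomized clinical trial with two parallel groups". Section 2.2: "The randomization will be at group level to avoid contamination between members of the same rehabilitation group". The sample size in section 2.3 follows from that design and is computed "with a conservative assumption that the intraclass correlation is 0.2 and the coefficient of variation in cluster size up to 0.7".

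The primary analysis in section 5.2 does not follow it: "The model will include participant ID as a random effect and time", the interaction of time with group and the baseline covariates as fixed effects. The covariates are age, sex and education. The group in the interaction is the treatment arm; rehabilitation group is not a term, and no cluster-adjusted variance is given.

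Section 5.2.1 brings rehabilitation group in as a third level, but only as a secondary check: "We do not anticipate strong cluster-level effects; however, we will conduct a sensitivity analysis including rehabilitation group in the mixed linear model".

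Section 3.1 sets the form of the headline result: "We will use two-sided tests and report mean differences with 95% confidence intervals". For continuous secondary outcomes section 5.3 says only "For the other secondary outcomes, a mixed linear regression model will be used", without naming the random effects.

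**The concern.** Whole rehabilitation groups are assigned to an arm, so the treatment contrast is a contrast between groups. Its variance includes whatever the members of a group share. A model with a participant intercept only counts about 75 to 105 people as independently randomised, when 15 to 21 groups were. If the shared component is above zero, the standard error is too small, the 95% CI covers less than 95%, and the null is rejected too often.

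The result at stake is the main one: the ISI difference at 3 months with its CI and p-value. The three-level sensitivity analysis lets a reader see both answers, but the trial's primary conclusion would still come from the model that omits the randomised unit.

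**Working it through.** **Inputs from SAP section 2.3.** SD 4, difference 4 points, two-sided 5% level, 15 clusters at 2:1, N = 50 + 25 = 75, ICC 0.2, CV of cluster size up to 0.7, stated power 80%, 21 clusters to be recruited, dropout about 20%. Mean cluster size m = 75/15 = 5; after 20% dropout, 5 × 0.8 = 4. At 2:1, 21 clusters split 14:7.

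**Step 1: the plan's own power figure.** Without clustering, SE = 4 × √(1/50 + 1/25) = 0.98 and power is 98.3%. For a random-effects analysis with unequal clusters, the design effect is DE = [1 + (m−1)ICC] / [1 − CV²L(1−L)], with L = m·ICC/(m·ICC + 1 − ICC) = 1/1.8 = 0.556. So DE = 1.80/(1 − 0.49 × 0.247) = 2.05, SE = 0.98 × √2.05 = 1.40, and power = Φ(4/1.40 − 1.96) = 81%. The stated 80% is reproduced, and only by allowing for clustering.

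**Step 2: type I error if the cluster is ignored.** Here DE = 1 + [(1 + CV²)m − 1]·ICC, and type I error = 2[1 − Φ(1.96/√DE)]. Example: m = 5, CV 0.7, ICC 0.2 gives DE = 1 + (1.49 × 5 − 1) × 0.2 = 2.29, 1.96/√2.29 = 1.295, error 19.5%.

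| ICC | m=4, CV 0 | m=4, CV 0.7 | m=5, CV 0 | m=5, CV 0.7 |
|---|---|---|---|---|
| 0.01 | 5.3% | 5.6% | 5.5% | 5.8% |
| 0.05 | 6.8% | 7.9% | 7.4% | 8.8% |
| 0.1 | 8.6% | 10.9% | 9.8% | 12.7% |
| 0.2 | 12.1% | 16.5% | 14.4% | 19.5% |

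At m = 5 and ICC 0.2 the nominal 95% CI covers 85.6% (CV 0) to 80.5% (CV 0.7).

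**Step 3: does recruiting 21 clusters help?** No. The model SE falls to 4 × √(1/70 + 1/35) = 0.83, but the true SE is 1.11 (CV 0) or 1.25 (CV 0.7), so the ratio is unchanged. A null simulation (complete data, three follow-ups, 10,000 trials per setting, participant share of variance assumed to be 0.4) gave 14.7-19.4% with 15 clusters and 15.0-19.1% with 21, at ICC 0.2.

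**Step 4: fitted mixed models, and the role of baseline ISI.** Assumptions: 14:7 groups, mean 5 per group, REML with participant intercept, time and time-by-arm, Wald z, 4,000 replicates per cell. Within-person correlation 0.6 and 20% missing at random at each visit are assumed, and covariates are omitted. Type I error for CV 0 / CV 0.7:

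| ICC | No baseline ISI | Baseline as response, group effect already at baseline | Baseline as response, group effect only afterwards |
|---|---|---|---|
| 0 | 5.3 / 5.4% | 5.2 / 5.1% | 5.1 / 5.3% |
| 0.05 | 7.5 / 8.9% | 5.7 / 6.1% | 7.8 / 9.7% |
| 0.2 | 14.3 / 18.0% | 6.7 / 8.2% | 15.8 / 20.7% |

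At ICC 0.01 without baseline the simulation gave 5.3 / 5.2%, indistinguishable from ICC 0. At ICC 0.2 without baseline the mean model SE was 0.88-0.90 against a true SD of 1.16-1.30. Since 0.88/1.16 = 0.76 and 0.90/1.30 = 0.69, the CI is 24-31% too narrow.

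**Step 5: does respecting the cluster cure it?** In the Step 4 settings a t-test on cluster means rejected in 4.3-5.4% of trials in every cell. The three-level REML model without baseline (2,000 replicates) rejected in 2.9-4.8% with t on 19 df (21 − 2), over ICC 0, 0.05 and 0.2. With uncorrected Wald z it reached 6.5% at ICC 0.2, CV 0.7, so a small-sample correction is needed.

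**The case against.** The best defence is that the sponsor expects weak clustering, calls ICC 0.2 conservative, and has pre-specified the three-level model; section 3.4.2 also promises published analysis syntax. Planning for a cautious upper value while expecting less is coherent, so this is not a flat contradiction. It does mean that 12.1-19.5% is an upper planning range rather than a forecast, and that the ICC 0.01 to 0.1 rows matter at least as much. At ICC 0.01 the inflation is negligible.

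The size also depends on a choice the SAP leaves open. Section 5.2 lists time and the interaction without an arm main effect, which is compatible with baseline ISI as a response. If group differences were already present at baseline, that form limits the error to about 7-8% at ICC 0.2. But the groups are treated together after baseline, so later group effects are plausible, and for those the form gives no protection.

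It can be said that no tie-breaking rule is missing, because the labels primary and sensitivity already imply that the participant-only result stands. That is fair, and it is the difficulty: the result that stands is the one without the randomised unit.

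None of this makes the primary interval valid when the ICC is positive. An expectation of weak clustering is not a substitute for modelling it, and ICC 0.05 already gives about 7-9% without baseline ISI.

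**Conclusion.** The concern holds. The primary model as written omits the unit of randomisation, and its p-value and CI are anti-conservative whenever outcomes correlate within rehabilitation groups. How much depends on an ICC that the SAP does not estimate: nothing at zero, and 12.1-19.5% type I error at the planning value, for 4 to 5 analysed per group, CV 0 to 0.7 and baseline ISI not modelled. The simulated figures rest on the assumed within-person correlation and missingness; the formula results do not. The power claim allows for clustering that the primary analysis then ignores. For continuous secondary outcomes the point is open, because section 5.3 does not state the random effects. This should be corrected before unblinding.

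**What to change.** - In section 5.2, make the three-level model of section 5.2.1 (time within participant within rehabilitation group) the primary analysis, whatever ICC is estimated.
- Specify a small-sample correction for about 21 groups, for example REML with Kenward-Roger or Satterthwaite degrees of freedom, or use a cluster-level summary analysis. The versions checked above were t on 19 df and the cluster-mean t-test; Kenward-Roger and Satterthwaite were not simulated.
- Move the participant-only model to sensitivity or drop it, and state that the three-level result stands if the two differ.
- State whether and how baseline ISI enters the model.
- In section 5.3, name the random effects for continuous secondary outcomes and include the same rehabilitation-group effect.

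The cost is wording: the sponsor has already written the model, no new data are needed, and section 5.2 already foresees an updated SAP before unblinding. If the published protocol, not seen here, describes the participant-only model, the change should be reported as a departure from it. In simulation the mean SE rises by no more than about 5% if the true ICC is 0 (0.89 to 0.92 with equal groups, about 3% on these rounded values). At ICC 0.2 it rises by about 31-34% (for example 0.88 to 1.15, and 1.15/0.88 = 1.31), where the narrower interval was wrong.

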## STATISTICAL ANALYSIS PLAN for “Digital sleep therapy in patients with Musculoskeletal complaints and insomnia”

### 1. Introduction

This Statistical Analysis Plan (SAP) should be read in conjunction with the published trial protocol: *App-Delivered Cognitive-Behavioral Therapy for Insomnia Among Patients with Comorbid Musculoskeletal Complaints and Insomnia Referred to 4-Week Inpatient Multimodal Rehabilitation: Protocol for a Randomized Clinical Trial* [1]. The information available here provides a more detailed description of the “Statistical analysis” section.

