#### 1.1 Purpose and scope of the statistical analysis plan

This document details the proposed analyses of the main paper reporting results from the study *“Digital sleep therapy in patients with musculoskeletal complaints and insomnia referred to inpatient multimodal pain rehabilitation”*. Any deviations from the analyses outlined in this SAP will be described and justified in the final report of the trial, including the inclusion of any analyses suggested by journal editors and referees. Modifications will be carefully considered and, as far as possible, follow the broad principles set out here.

First and foremost, this SAP describes the analysis of the primary and secondary outcomes. Subsequent exploratory analyses are also expected to follow the broad principles of this SAP but are not described in detail here.

The details presented here shall not prohibit accepted practices, such as data transformation prior to analysis. When possible, such data management and modelling decisions will be undertaken prior to revealing the treatment allocation. The final analysis strategy will be available on request when the papers are submitted.

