#### **Questionnaires**

Self-reported web-based questionnaires are answered at five time points: at baseline (prior to randomization), 6 weeks (at the end of rehabilitation), at 3 months (primary outcome measurement), 6 months, and 12 months after end of rehabilitation.

In addition, diagnoses and use of medication at baseline will be available through the electronic patient records.

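### SAP 5.2 does not say whether baseline ISI enters the primary model; unless a common baseline mean is intended, the 3-month difference goes unadjusted for it and loses precision

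*SAP*

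**What the plan says.** Section 5.2 uses a linear mixed model to "estimate mean difference in ISI between the two groups at 3, 6 and 12 months of follow-up", with 3 months as the primary time. The terms are "participant ID as a random effect and time, time–group interaction and baseline covariates as fixed effects". The covariates are then listed: "Of baseline covariates we will include age, sex, and education". No group main effect is named, and baseline ISI is not mentioned.

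Section 5.2.1 describes the three-level sensitivity model "with follow-up timepoints as level 1", with participants and rehabilitation groups above them.

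The baseline score is available. The Questionnaires paragraph in 2.7.1 has questionnaires answered "at baseline (prior to randomization), 6 weeks (at the end of rehabilitation), at 3 months (primary outcome measurement") and again at 6 and 12 months, and Table 1 marks ISI at every one of these times. Section 5.3 says only that the remaining secondary outcomes get a mixed linear model.

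The Introduction points to the published protocol, but says of the SAP: "The information available here provides a more detailed description of the" protocol's statistical analysis section. The handling of baseline ISI therefore belongs here.

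**The concern.** The baseline value of the primary outcome is usually among the strongest predictors of its follow-up value. A model that holds age, sex and education but not baseline ISI leaves that information unused. The confidence interval is then wider than it need be, and a chance difference in baseline ISI between arms passes in part into the reported effect. With about 21 clusters at 2:1 (about 14 against 7), such a difference is not remote.

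The wording also allows models that give different estimates and standard errors from the same data. A reader cannot tell from 5.2 which one will be the primary result.

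**Working it through.** **Three models that fit the text**

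- A: outcome rows are follow-up scores only, with one group contrast per time. This is suggested by the estimation times in 5.2 and by "with follow-up timepoints as level 1" in 5.2.1.
- B: baseline is an additional outcome row with its own group contrast.
- C: baseline is an outcome row with one mean common to both arms, and time-by-group terms only after baseline. The absence of a group main effect would fit this.

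Time plus time-by-group without a group main effect is the usual way to write C. It can also be a coding of A or B with a separate contrast at each time.

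**The plan's own power figure**

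Inputs from SAP 2.3: 15 clusters at 2:1 (10 and 5), expected sample 50 and 25 (mean cluster size m = 5), SD 4, difference 4, ICC 0.2, CV of cluster size 0.7, 5% level. Two-sided testing is from 2.4.

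- L = m·ICC/(m·ICC + 1 − ICC) = 1/1.8 = 0.556
- Design effect = [1 + (m − 1)ICC]/[1 − CV²·L(1 − L)] = 1.8/0.879 = 2.048
- SE = 4·sqrt(2.048·(1/50 + 1/25)) = 1.402
- Power = Φ(4/1.402 − 1.96) = 81.4%, against the stated 80%

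The SAP does not name its method. The cruder design effect 1 + ((1 + CV²)m − 1)ICC = 2.29 gives 77.0%, and a t reference on 13 df with 2.048 gives 75.1%. None of these uses baseline adjustment, so the stated power does not rest on it.

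**Effect of adjustment on the 3-month contrast**

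Assumptions: equal SD 4 at all times and one correlation r between any two times. The SAP gives no r, baseline SD or baseline ICC. The planned 21 clusters of about 5 give 14·5 = 70 and 7·5 = 35 participants. Generalised least squares puts weight 0 on the baseline difference under A and B, and −r under C. With complete data, SE(A) = SE(B) = 4·sqrt(1/70 + 1/35) = 0.828, and SE(C) = 0.828·sqrt(1 − r²). Baseline ISI as a covariate gives the same result as C.

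| | r = 0.3 | r = 0.5 | r = 0.7 |
|---|---|---|---|
| SE multiplier sqrt(1 − r²) | 0.95 | 0.87 | 0.71 |
| Variance reduction | 9% | 25% | 49% |
| ICC 0: SE 0.83 falls to | 0.79 | 0.72 | 0.59 |
| ICC 0.2, CV 0.7: SE 1.19 falls to | 1.13 | 1.03 | 0.85 |

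The last row further assumes the same r between and within clusters.

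With the expected 20% dropout (56 and 28 followed up, ICC 0), SE(A) = 4·sqrt(1/56 + 1/28) = 0.926:

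| | r = 0.3 | r = 0.5 | r = 0.7 |
|---|---|---|---|
| B | 0.917 | 0.902 | 0.879 |
| Variance change, B against A | −2% | −5% | −10% |
| C or covariate | 0.883 | 0.802 | 0.661 |
| Variance change, C against A | −9% | −25% | −49% |

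So B recovers only a small part of the gain. A small simulation with complete data (60 runs, r = 0.5, 50 against 25) agreed: A and B gave the same mean and spread (empirical SD 1.09), and C matched the covariate form (0.898 and 0.894).

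**Chance baseline imbalance, 70 against 35**

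SE of the baseline difference = SD·sqrt(DE·(1/70 + 1/35)); the probability is two-sided normal.

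| Assumed baseline SD and clustering | SE | P(difference above 1 point) |
|---|---|---|
| SD 3, ICC 0 | 0.621 | 11% |
| SD 4, ICC 0 | 0.828 | 23% |
| SD 3, ICC 0.2, CV 0.7 | 0.889 | 26% |
| SD 4, ICC 0.2, CV 0.7 | 1.185 | 40% |

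The last row is an upper end. SD 4 belongs to the statement that "the average Insomnia Severity Index (ISI)-score for participants completing usual treatment will be 15", not to baseline, and 2.3 calls the ICC of 0.2 conservative. At equal SDs, a 1-point imbalance is expected to move the unadjusted 3-month difference by r points (0.3, 0.5 or 0.7), against the 4-point target.

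**The case against.** The strongest objection is that 5.2 may already adjust. Its term list has no group main effect, which is the usual form of a common-baseline model. With product terms and a reference time, leaving out the group term forces a zero difference at that reference. That is sensible if the reference is baseline, and awkward if it is a follow-up time. The times in "estimate mean difference in ISI between the two groups at 3, 6 and 12 months of follow-up" say where differences are estimated, not which rows are fitted, and the level-1 wording belongs to a sensitivity model. This stands as far as it goes: a reader might infer that the plan certainly ignores baseline ISI, and the text does not support that. Nor does it support the opposite, because no common baseline mean is stated.

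Second, the size of the gain rests on an assumed r. Participants are selected for insomnia, which may restrict the range of baseline scores and lower r; at r = 0.3 the standard error falls by only about 5%. This also stands.

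Third, the SAP has safeguards. On modelling choices, 1.1 says: "When possible, such data management and modelling decisions will be undertaken prior to revealing the treatment allocation". Section 3.4.2 has the syntax for the main analyses published before they are run. A reader might infer that the gap leaves the model open to choice after seeing results; these provisions largely answer that. They do not make the model adjust for baseline ISI. The updated SAP foreseen in 5.2 concerns only the categorisation of covariates.

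**Conclusion.** The point holds as one of specification and efficiency. Section 5.2 does not state how baseline ISI is used, and two of the three models that fit its wording leave the 3-month difference unadjusted, or nearly so with dropout. Under those two, adjustment multiplies the SE by about 0.95, 0.87 or 0.71 at assumed r = 0.3, 0.5 or 0.7, less the small part that B already recovers with dropout. Under the third, the gain is already there and only needs to be stated.

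A reader might go further and infer that the primary analysis is biased or underpowered. Neither follows. The unadjusted difference is unbiased over randomisations, and the stated 80% can be approximately reproduced without adjustment. The figures assume equal SDs and one correlation over time; the clustered ones also assume the same r at both levels. The plan should be changed on this point, but its validity is not in question.

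**What to change.** In 5.2, add baseline ISI as a fixed covariate beside age, sex and education, with outcome rows at follow-up only. Alternatively, if a common-baseline model is intended, state that baseline is a level of time with one mean for both arms and that time-by-group terms enter only after baseline. The planned participant random intercept can stay in either case; an unstructured covariance is not required. Choose one form, so that baseline ISI is not both covariate and outcome row.

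In 5.3, adjust each continuous secondary outcome for its own baseline value in the same way. Table 1 shows that pain, fatigue, EQ-5D, PSFS and physical activity are all measured at baseline.

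The cost is one sentence in each section and, for the covariate form, one degree of freedom per model. No new data are needed. The change can go into the updated SAP that 5.2 already foresees before unblinding, and into the published syntax.
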